#### 11.1.2 Serious Adverse Event

A SAE is an adverse event that results in any of the following outcomes:

- Death
- Is life-threatening (subject is at immediate risk of death at the time of the event; it does not refer to an event that hypothetically might have caused death if it were more severe)
- Requires in-subject hospitalization (formal admission to a hospital for medical reasons) or prolongation of existing hospitalization
- Results in persistent or significant disability/incapacity (i.e., there is a substantial disruption of a person’s ability to carry out normal life functions)
- Is a congenital anomaly/birth defect
- Is an important medical event

Important medical events that may not result in death, are not life-threatening, or do not require hospitalization may be considered an SAE when, based upon appropriate medical judgment, they may jeopardize the subject or may require medical or surgical intervention to prevent one of the

outcomes listed in this definition. Examples of such events include allergic bronchospasm requiring intensive treatment in an emergency room or at home, blood dyscrasias or convulsions that do not result in subject hospitalization, or the development of drug dependency or drug abuse.

In addition Suspected Unexpected Serious Adverse Reactions (SUSAR) may also be reported to competent authorities where this type of reporting is required (e.g. European Union Directives). See section 11.2.3.

## 11.2 Method, Frequency, and Time Period for Detecting Adverse Events and Reporting Serious Adverse Events

Reports of AEs are to be collected from the time of study drug administration through the follow-up period ending on Day 14. The Investigator or designee must completely and promptly record each AE on the appropriate CRF. The Investigator should attempt, if possible, to establish a diagnosis based on the presenting signs and symptoms. In such cases, the diagnosis should be documented as the AE and not the individual sign/symptom. If a clear diagnosis cannot be established, each sign and symptom must be recorded individually.

The Investigator should attempt to follow all unresolved AEs and/or SAEs observed during the study until they are resolved, or are judged medically stable, or are otherwise medically explained.

### 11.2.1 Definition of Severity

All AEs will be assessed (graded) for severity and classified into one of four clearly defined categories as follows:

- **Mild:** (Grade 1): Transient or mild symptoms; no limitation in activity; no intervention required. The AE does not interfere with the participant's normal functioning level. It may be an annoyance.
- **Moderate:** (Grade 2): Symptom results in mild to moderate limitation in activity; no or minimal intervention required. The AE produces some impairment of functioning, but it is not hazardous to health. It is uncomfortable or an embarrassment.
- **Severe:** (Grade 3): Symptom results in significant limitation in activity; medical intervention may be required. The AE produces significant impairment of functioning or incapacitation.
- **Life-threatening:** (Grade 4): Extreme limitation in activity, significant assistance required; significant medical intervention or therapy required; hospitalization.

### 11.2.2 Definition of Relationship to Study Drug

The blinded Principal Investigator must review each AE and make the determination of relationship to study drug using the following guidelines:

- Not Related:** The event can be readily explained by other factors such as the subject's underlying medical condition, concomitant therapy, or accident, and no temporal relationship exists between the study drug and the event.
- Unlikely:** The event does not follow a reasonable temporal sequence from drug administration and is readily explained by the subject's clinical state or by other modes of therapy administered to the subject.
- Possibly Related:** There is some temporal relationship between the event and the administration of the study drug and the event is unlikely to be explained by the subject's medical condition, other therapies, or accident.
- Probably Related:** The event follows a reasonable temporal sequence from drug administration, abates upon discontinuation of the drug, and cannot be reasonably explained by the known characteristics of the subject's clinical state.
- Definitely Related:** The event follows a reasonable temporal sequence from administration of the medication, follows a known or suspected response pattern to the medication, is confirmed by improvement upon stopping the medication (dechallenge), and reappears upon repeated exposure (rechallenge, if rechallenge is medically appropriate).

### 11.2.3 Reporting Serious Adverse Events

Any SAE / SUSAR (Suspected Unexpected Serious Adverse Reaction) must be reported to BioCryst or its designee within 24 hours of the Investigator's recognition of the SAE by first notifying the Medical Monitor at the number listed below:

Telephone: **Europe: [name]; North America: [name]**

Facsimile: **Europe: [name]; North America: [name]  
or [name]**

In addition to the telephone numbers listed above, local country-specific toll free numbers may be provided within the study reference manual.

The site is required to fax a completed SAE / SUSAR Report Form (provided as a separate report form) within 24 hours. All additional follow-up evaluations of the SAE / SUSAR must be reported and sent by facsimile to BioCryst or its designee as soon as they are available.

The Principal Investigator or designee at each site is responsible for submitting the IND safety report (initial and follow-up) or other safety information (e.g., revised Investigator's Brochure) to the Institutional Review Board/Independent Ethics Committee (IRB/IEC) and for retaining a copy in their files.

If the Investigator becomes aware of any SAE / SUSAR occurring within 30 days after a subject has completed or withdrawn from the study, he or she should notify BioCryst or its designee.

Any SAEs / SUSARs considered possibly related to treatment will be reported to the FDA and other Regulatory Competent Authorities as applicable via the MedWatch / CIOMS reporting system in accordance with FDA and other applicable regulations. However, the Investigator is not obligated to actively seek reports of AEs in former study participants.

While pregnancy is not considered an AE, all cases of fetal drug exposure via parent as study participant (see Section 4.4) are to be reported immediately to BioCryst or its designee. Information related to the pregnancy must be given on a "Pregnancy Confirmation and Outcome" form that will be provided by the Sponsor or its designee.

#### **11.2.4 Emergency Procedures**

In the event of an SAE / SUSAR, the Principal Investigator may request the unblinding of the treatment assignment for the subject affected. If time allows (i.e., if appropriate treatment for the SAE is not impeded), the Principal Investigator will first consult with the Medical Monitor regarding the need to unblind the treatment assignment for the subject. At all times, the clinical well-being of any subject outweighs the need to consult with the Medical Monitor.

The Principal Investigator may contact the IVRS central randomization center and request the unblinding of the treatment assignment that corresponds to the affected subject. The IVRS center will record the name of the Investigator making the request, the date and time of the request, the subject number and date of birth. The Sponsor will be informed within 24 hours if unblinding occurred.

## **12 STATISTICAL METHODS**

Descriptive statistical methods will be used to summarize the data from this study, with hypothesis testing performed for the primary and other selected efficacy endpoints. Unless stated otherwise, the term "descriptive statistics" refers to number of subjects (n), mean, median, standard deviation (SD), minimum, and maximum for continuous data and frequencies and percentages for categorical data. The term "treatment group" refers to randomized treatment assignment: peramivir 300 mg or placebo. All data collected during the study will be included in data listings. Unless otherwise noted, the data will be sorted first by treatment assignment, subject number, and then by date within each subject number.

Unless specified otherwise, all statistical testing will be two-sided and will be performed using a significance (alpha) level of 0.05.

All statistical analyses will be conducted with the SAS® System, version 9.1.3 or higher.

### **12.1 Data Collection Methods**

The data will be recorded on the CRF approved by BioCryst. All documentation supporting the CRF data, such as laboratory or hospital records, must be readily available to verify entries in the CRF.

Documents (including laboratory reports, hospital records subsequent to SAEs, etc.) transmitted to BioCryst should not carry the subject's name. This will help to ensure subject confidentiality.

## 12.2 Statistical Analysis Plan

A statistical analysis plan (SAP) will be created and approved prior to the review of any data. This document will provide a more technical and detailed description of the proposed data analysis methods and procedures.

## 12.3 Study Hypothesis

The primary hypothesis for evaluating the primary objective may be stated as follows:

The null hypothesis ( $H_0$ ) is that the time to alleviation of influenza symptoms is the same for subjects treated with placebo and for subjects treated with peramivir 300mg.

The alternative hypothesis ( $H_1$ ) is that subjects treated with peramivir 300mg have an improvement in time to alleviation of influenza symptoms over those treated with placebo.

## 12.4 Sample Size Estimates

From preliminary results of a phase 2 study evaluating peramivir treatment of uncomplicated influenza, it is expected that the median time to alleviation of symptoms will be 137.0 hours (95% CI: 115.9, 165.8) for subjects receiving placebo treatment. Additionally, it is expected that the median time to alleviation for the 300 mg dose peramivir arm will be reduced by 30% compared to placebo yielding a hazard ratio of 0.70. Data from the phase 2 study suggested that the activity of peramivir against influenza B was limited. Therefore, this study will be sized to ensure that a minimum number of influenza A subjects is enrolled to achieve study power.

Using these assumptions, a sample size of 450 evaluable subjects with influenza A (300 in the 300 mg treatment group and 150 evaluable subjects in the placebo group) is sufficient to provide at least 90% power to detect a hazard ratio of 0.70 using a log-rank statistic and  $\alpha = 0.05$  (SAS version 9.1.3; total accrual time 7 months; total enrollment time 6 months).

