	
for the 300 mg dose peramivir arm will be reduced by 30% compared to placebo yielding a hazard ratio of 0.70. Data from the phase 2 study suggested that the activity of peramivir against influenza B was limited. Therefore, this study will be sized to ensure that a minimum number of influenza A subjects is enrolled to achieve study power.
 
Using these assumptions, a sample size of 450 evaluable subjects with influenza A (300 in the 300 mg treatment group and 150 evaluable subjects in the placebo group) is sufficient to provide at least 90% power to detect a hazard ratio of 0.70 using a log-rank statistic and <math>\alpha = 0.05</math> (SAS version 9.1.3; total accrual time 7 months; total enrollment time 6 months).

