
Efficacy:
	
The primary efficacy analysis will be completed with the intent-to-treat infected population (ITTI). The ITTI population will include all subjects who are randomized, received study drug, and have confirmed influenza A and/or B by primary viral culture or PCR. The primary efficacy variable is the time to alleviation of symptoms, defined as the time from injection of study drug to the start of the time period when each of seven symptoms of influenza are either absent or are present at no more than mild severity level and remain at no worse than this severity status for a 21.5 hour (24 hours – 10%) period.
 
Descriptive statistics for the primary efficacy variable will be tabulated by treatment group. Alleviation of symptoms will be determined by assessment of symptoms as reported on each subject's diary card. Time to alleviation of symptoms will be summarized for each treatment group. Treatment differences between the 300 mg peramivir dose and placebo will be assessed using a Wilcoxon-Gehan statistic stratified by smoking status and positive PCR or viral culture for influenza A or B at screening. Subjects who do not experience alleviation of symptoms will be censored at the date of their last non-missing assessment.
 
Efficacy analyses will be repeated for Intent To Treat Infected with influenza A (ITTI-A) population and Per-Protocol Infected population (PPI). The ITTI-A population includes all subjects who are randomized, received study drug, and have confirmed influenza A by primary viral culture or PCR. The PPI population will include those subjects in the ITTI population who received an adequate intramuscular injection. Details of this population will be described in the statistical analysis plan.
 
Changes in influenza virus TCID50 (viral titers from nasopharyngeal specimens) will be compared using the van Elteren statistic controlling for smoking status and positive PCR or viral culture for influenza A or B at screening. Analyses of other continuous endpoints will be analyzed in a similar manner.

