A sub group of subjects was identified in which a Day 3 CK increase of at least 50U/L was observed over baseline. Within this adequate intramuscular injection sub-group, notable improvements in the time to alleviation of symptoms were observed for both peramivir dose groups: 44.6 hours for peramivir 150 mg treatment and 64.8 hours for the peramivir 300 mg treatment (**Table 3**). A further sub-group analysis suggested that in subjects with an influenza B infection confirmed by PCR a single dose of peramivir had limited activity (**Table 3**). These efficacy data support the further development of peramivir as a single dose, intramuscular treatment for acute influenza.

Table 3 Summary of Efficacy from BCX1812-211.

	Placebo	Peramivir 150mg	Peramivir 300mg
Intent-to-Treat Infected Population  (n=313)	n=107	n=104	n=102
Median time to alleviation of symptoms (hrs)	137.0	114.1	115.9
(95% Confidence Interval)	115.9-163.8	95.2-145.5	77.8-136.6
Improvement over Placebo (hrs)		22.9	21.1
Adequate Injection Population  (n=101)	n=40	n=32	n=29
Median time to alleviation of symptoms (hrs)	152.2	107.6	87.4
(95% Confidence Interval)	103.8-183.9	76.8-175.1	40.8-163.8
Improvement over Placebo (hrs)		44.6	64.8
ITTI Influenza A infected population (n=247)	n=83	n=85	n=79
Median time to alleviation of symptoms (hrs)	138.4	115.7	115.9
(95% Confidence Interval)	117.0-173.4	92.2-145.5	51.1-195.9
Improvement over Placebo (hrs)		22.7	22.5
ITTI Influenza B infected population (n=66)	n=24	n=19	n=23
Median time to alleviation of symptoms (hrs)	117.1	100.8	123.3
(95% Confidence Interval)	100.3-162.3	68.2-162.0	67.5-178.7
Improvement over Placebo (hrs)		16.3	-6.2
 : Intent-to-Treat Infected Population: PCR+ for either Influenza A and/or Influenza B at baseline/screening visit.			
 : Adequate Injection Population: ITTI subjects in who study drug reached target muscle tissue, as evidenced by an increase in serum CK levels of $\geq 50$ U/L over baseline at the Day 3 study visit.			

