## 12.5 Analysis Populations

The populations for analysis will include the intent-to-treat (ITT), intent-to-treat infected (ITTI and ITTI-A), per-protocol infected (PPI), and safety populations. Additional analysis populations may be defined to evaluate study results. Any additional analysis populations will be defined in the SAP.

**Intent-To-Treat Population:** The ITT population will include all subjects who are randomized. Subjects will be analyzed in the treatment group to which they were randomized. The ITT population will be used for analyses of accountability and demographics.

**Intent-To-Treat Infected Population:** The ITTI population will include all subjects who are randomized, received study drug, and have confirmed influenza by culture or PCR. Subjects will be analyzed according to the treatment randomized. If a discrepancy is noted in the final database for any subject, such that the drug differs from the randomized treatment assignment, efficacy analyses may be repeated with the subjects analyzed according to the treatment received. The ITTI population will be used for primary analyses of efficacy.

**Intent-To-Treat Infected Population-A:** The ITTI-A population will include all subjects who

are randomized, received study drug, and have confirmed influenza A by culture or PCR. Subjects will be analyzed according to the treatment randomized. If a discrepancy is noted in the final database for any subject, such that the drug differs from the randomized treatment assignment, efficacy analyses may be repeated with the subjects analyzed according to the treatment received. The ITTI-A population will be used for supportive analyses of efficacy.

**Per-Protocol Infected:** The PPI population includes all subjects in the ITTI population who receive an adequate intramuscular injection. The definition of an adequate intramuscular injection will be further described in the SAP. The PPI population will be used for supportive analyses of efficacy.

**Safety Population:** The safety population will include all subjects who received study drug. Subjects will be analyzed according to the treatment received. This population will be used for all safety analyses.

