## 12.7 Efficacy Analyses

### 12.7.1 Primary Efficacy Endpoint

The primary efficacy endpoint is the time to alleviation of symptoms of influenza in subjects diagnosed with influenza, defined as the time from injection of study drug to the start of the time period when a subject has Alleviation of Symptoms. A subject has Alleviation of Symptoms if all of the seven symptoms of influenza (nasal congestion, sore throat, cough, aches and pains, fatigue (tiredness), headache, feeling feverish) assessed on his/her subject diary are either absent or are present at no more than mild severity level and at this status for at least 21.5 hours (24 hours - 10%).

Descriptive statistics for the primary efficacy variable will be tabulated by treatment group. Alleviation of symptoms will be determined by assessment of symptoms as reported on each subject's diary card. Time to alleviation of symptoms will be summarized for each treatment group (300 mg peramivir and placebo). Treatment comparisons between the 300 mg peramivir group and placebo will be assessed using a Wilcoxon-Gehan statistic stratified by smoking status and positive PCR or viral culture for influenza A or B at screening for the ITTI and PPI populations. Subjects who do not experience alleviation of symptoms will be censored at the date of their last non-missing post-baseline assessment.

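### The 90% power in section 12.4 is for a log-rank test in influenza A. The primary analysis, a stratified Wilcoxon-Gehan test in ITTI, has no stated power (about 84–85% in those same 450 subjects under the plan's hazard ratio)

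*Combined protocol and SAP*

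**What the plan says.** All references are to protocol Version 4.0 (18 December 2007).

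- **Sizing (section 12.4).** The placebo median is 137.0 hours, and the 300 mg arm's median is expected to be "reduced by 30% compared to placebo yielding a hazard ratio of 0.70". The calculation uses 450 evaluable subjects with influenza A, 300 on peramivir and 150 on placebo, and alpha 0.05. The conclusion is that this number "is sufficient to provide at least 90% power to detect a hazard ratio of 0.70 using a log-rank statistic". The synopsis (Sample Size) repeats "at least 90% power to detect a hazard ratio of 0.70 using a log-rank statistic". Section 12 adds that "all statistical testing will be two-sided and will be performed using a significance (alpha) level of 0.05".
- **Primary test (section 12.7.1).** The Wilcoxon-Gehan test is named, described as: "statistic stratified by smoking status and positive PCR or viral culture for influenza A or B at screening for the ITTI and PPI populations". The synopsis (Efficacy) agrees: the treatment difference "will be assessed using a Wilcoxon-Gehan statistic stratified by smoking status" and by influenza type.
- **Primary population (section 12.5).** "The ITTI population will be used for primary analyses of efficacy". The synopsis defines ITTI as confirmed influenza A and/or B. The influenza A subset, ITTI-A, is supportive only.
- **Influenza B.** Section 12.4 describes the activity of peramivir against type B as limited and gives that as the reason for sizing on type A. It states neither a number of B subjects nor an effect in them.

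**The concern.** The power statement and the primary analysis differ in two respects.

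1. **Test.** The log-rank test weights every event time equally. The Gehan test weights each event time by the number still at risk, so late events count less. When the hazard ratio is constant, which is the alternative that section 12.4 uses, the log-rank is the efficient choice and Gehan loses power.
2. **Population.** The trial is sized on influenza A, but the primary analysis includes influenza B, where the plan itself expects a weaker effect. Adding B subjects can raise or lower the power, depending on their number and response.

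The plan has only one power figure, so a reader will naturally attach it to the primary analysis. At stake is whether the sponsor and the trial's reviewers know the real chance of a positive primary result.

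**Working it through.** **Inputs from the documents.** Section 12.4: hazard ratio 0.70, placebo median 137.0 h, 300 vs 150 subjects, alpha 0.05 (two-sided by section 12). Peramivir median: 0.70 × 137.0 = 95.9 h. Follow-up: the symptom diary runs through Day 14 (section 7.1), about 336 h. Phase 2 type mix: 247 influenza A and 66 influenza B among 313 ITTI subjects (section 5.6, Table 3). **Assumed:** exponential times, and the smoking prevalences and influenza B effects stated below.

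**Step 1: reproduce the stated 90%.** Schoenfeld's formula for 2:1 allocation gives events needed = (1.960 + 1.282)² / [(1/3)(2/3)(ln 0.70)²] = 372. Events expected by 336 h:

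- Placebo: 150 × (1 − 2^(−336/137.0)) ≈ 122.6
- Peramivir: 300 × (1 − 2^(−336/95.9)) ≈ 273.5
- Total: about 396

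Power = Φ(√[396 × (2/9) × 0.1272] − 1.960) = 91.7%. With the plan's 7 months in total and 6 months of enrolment, almost every subject has an event (449.8), and power is 94.6%. The 90% therefore holds for the log-rank test in 450 influenza A subjects.

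**Step 2: the planned test in the same 450 subjects.** Let p₀, p₁ be the allocation fractions, S₀, S₁ the survival curves, λ₀, λ₁ the hazards, and y = p₀S₀ + p₁S₁. With weight w(t),

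μ = ∫ w p₀S₀p₁S₁/y · (λ₁ − λ₀) dt

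v = ∫ w² p₀S₀p₁S₁/y² · (p₀S₀λ₀ + p₁S₁λ₁) dt

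Power = Φ(√n · μ/√v − 1.960)

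Setting w = 1 (log-rank) gives 90.8% at 336 h. Setting w = y (Gehan) gives 84.2%.

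Independent simulations of 4,000 to 6,000 trials give 90.5–91.5% for the log-rank and 84.4–85.3% for Gehan. Variants of the Gehan result:

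- Two equal strata: 85.0%.
- Diary times rounded to 12 hours: 85.1%.
- 5% dropout (assumed): 84.3%.
- Smoking strata (15–35% smokers assumed): 84.2–85.0% with strata scaled by size, 80.4–82.5% with raw scores summed.
- No censoring: about 85%, against 94% for the log-rank. As a check, Noether's formula gives P = 1/1.70 = 0.588 and power Φ(√[12 × (1/3)(2/3) × 450] × 0.088 − 1.96) = 86.4%.

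By the same integral, Gehan reaches 90% at about 540 influenza A subjects (180:360).

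**Step 3: the ITTI population.** At the phase 2 mix, 247/313 = 78.9% are type A, so 450 type A subjects imply 450/0.789 ≈ 570 ITTI subjects, of whom 120 have type B. Stratified by type and smoking (25% assumed), 6,000 trials per setting, standard error about 0.5 points:

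| Hazard ratio in B | Log-rank | Gehan, strata scaled by size | Gehan, raw scores summed |
|---|---|---|---|
| 0.70 | 96% | 92% | 85% |
| 0.85 | 91% | 85% | 83% |
| 1.0 | 85% | 76% | 80% |

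Two repeat simulations agreed within about one point. Using the phase 2 placebo medians by type (138.4 h for A, 117.1 h for B) gives 92% / 85% (scaled / raw) at 0.70 in B and 75% / 79% at 1.0. Stratifying by type only, with raw sums and a hazard ratio of 1.0 in B, gives 83–85%. Under the null, every version rejected in favour of peramivir in 2.1–2.4% of trials, so the tests are valid.

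**Step 4: dependence on shape.** With the same 30% median reduction but a non-constant hazard ratio, the order reverses. Log-normal times (SD of log time 0.9, assumed) give Gehan 97% and log-rank 95%. Log-logistic times (scale 0.6, assumed) give 92% and 88%.

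**The case against.** Section 12.4 names its test and its population, and the number is correct for both. This is an incomplete power statement rather than an arithmetic mistake, and that description is fair.

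The 84–85% is not the power of the primary analysis either, because it pairs the primary test with a supportive population. The planning inputs are not specific to type A: 137.0 h is the phase 2 placebo median for all infected subjects. If hazard ratio 0.70 held throughout ITTI and strata were scaled by size, power would be 92% and the claim of at least 90% would be met. This stands, so the direction of the error in ITTI is not established. But it requires B to respond like A, which section 12.4 doubts and Table 3 does not support (300 mg was 6.2 h worse than placebo in B, n=66). With raw sums, the same case gives only 85%.

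The loss also depends on shape. The phase 2 placebo interval (115.9–163.8 h, n=107) has a half-width of 0.17 on the log scale, against about 0.27 for exponential times, which hints at a shape that favours Gehan. The 300 mg interval does fit exponential times, so the evidence is mixed. The criticism therefore applies only to the constant hazard ratio that the plan states.

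The figure of 120 B subjects is illustrative: it implies 570 of about 600 randomized are confirmed (95%), whereas phase 2 confirmed 313 of 344 (91%). Finally, section 12.2 defers detail to a separate SAP whose text was not supplied. Power or stratum weighting may be stated there, but that would not correct section 12.4 or the synopsis.

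**Conclusion.** The concern holds. The only stated power belongs to a different test and a different population from those of the primary analysis. Under the plan's constant hazard ratio of 0.70, with exponential times and follow-up to Day 14, the planned test has about 84–85% power in the 450 influenza A subjects, roughly 6 points below the log-rank.

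Power in ITTI could fall on either side of 90%. With 120 B subjects it ran from about 75% to 92% across the settings tried, depending on the effect in B and on how strata are combined. Confidence is high for the mismatch and for the influenza A figure. The ITTI figures are conditional on inputs that the supplied documents do not give. This should be corrected, but it does not threaten the validity of the test or the effect estimate.

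**What to change.** Keep Wilcoxon-Gehan as the primary test and rewrite the power statement in section 12.4 and in the synopsis.

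- **Influenza A.** Suggested text: *For 450 evaluable influenza A subjects (300:150), the stratified Wilcoxon-Gehan test has about 85% power at two-sided alpha 0.05 for a constant hazard ratio of 0.70 (exponential times, placebo median 137.0 h, follow-up to Day 14, stratum statistics scaled by stratum size).* The log-rank figure may stay if it is labelled as such.
- **ITTI.** State the expected number of influenza B subjects, the effect assumed in them, and the resulting power. The table above shows the form this could take. The sponsor should use its own inputs.
- **Strata.** Say how stratum statistics are combined, since this moves ITTI power by several points.
- **Optional.** Add a stratified log-rank test as a sensitivity analysis. Making it primary is possible but not required.

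The cost is wording only: the test, enrolment and data collection do not change. The stated influenza A power becomes less favourable, and the sponsor must commit to an assumption about influenza B. The correction itself needs no extra patients. If the sponsor wants 90% for the planned test in influenza A under constant hazards, about 540 such subjects would be needed, which is a separate decision.
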